11.4.3 Analyses of safety data

All safety analysis will be performed on the safety population.

11.4.3.1 Adverse events

Adverse events reported in this study will be coded using the version of the Medical Dictionary for Regulatory Activities in effect at Sanofi at the time of database lock. Adverse events occurred during the treatment-emergent period will be considered as TEAE.

11.4.3.1.1 Treatment-emergent adverse events

Incidence of TEAE and the number of TEAEs per 100 patient-years (total number of events adjusted for the total duration of exposure) will be presented by system organ class (SOC), high level group term (HLGT), and preferred term (PT) sorted in alphabetical order, the number and percentage (%) of patients experiencing a TEAE.

In the derivation of incidence of AEs, multiple occurrences of the same event in the same patient will be counted only once in the tables. The denominator will be based on the total number of patients in the safety population.

The proportion of patients with at least one TEAE, serious TEAE, and TEAE leading to discontinuation of the study will be tabulated. In addition TEAEs will be described according to maximum intensity and relationship to the study drug.

11.4.3.1.2 Adverse events

An overview summary will be presented of the number (%) of patients with:

- Any TEAE.
- Any SAE and AEs leading to death (regardless of treatment-emergent status).
- Any treatment-emergent SAEs.
- Any AE leading to permanent study discontinuation.

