2.1.4 Safety endpoints

Primary endpoint:

- Incidence rates, defined as the percentage of patients reporting any treatment-emergent adverse events (TEAEs), and event rates defined as number of TEAEs per 100 person-years.

Secondary endpoints:

- Incidence rates and event rates per 100 person-years for AESIs over the study.
- Incidence rates for SAEs/death over the study.
- Incidence rates for AEs leading to study discontinuation over the study.

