2.4.5.1 Analyses of adverse events

Analysis of Primary Safety Endpoint

Incidence rates of TEAEs with corresponding 95% CI (by the Clopper-Pearson method) will be calculated as follows:

- Incidence Rate (IR) = number patients with one or more TEAEs / number of subjects at risk (i.e. safety population) × 100

Event rates per 100 person-years of TEAEs with corresponding 95% CI (two-sided exact Poisson CIs) will be calculated. All events reported during the study follow-up period will be counted, regardless of whether they are reported in the same subject (i.e., multiple events per subjects), or different subjects. The person-years at follow-up will be calculated using the standard on-treatment duration formula: (the date of last IMP – date of first dose of IMP + 14 days)/365.25. Note that date of first dose of IMP, is in regards to first dose of this study, not first dose of the parent study. Event rate per person-years will be calculated as follows:

- Event rate (ER) = number of TEAEs / number of person-years at follow up

Analysis of Secondary Safety Endpoints

Incidence rates with corresponding 95% CI (Clopper-Pearson method) and event rates with corresponding 95% CI (exact Poisson method) will be presented for AESIs, described in [section 2.1.4.1](#), using the same methodology described above.

Incidence rates with corresponding 95% CI (Clopper-Pearson method) will be presented for SAEs/death over the study.

Incidence rates with corresponding 95% CI (Clopper-Pearson method) will be presented for AEs leading to study discontinuation over the study.

Generalities

The primary focus of adverse event reporting will be on treatment-emergent adverse events.

Statistical Analysis Plan
LPS15023 - Dupilumab

15-Mar-2021
Version number: 2.0

If an adverse event date/time of onset (occurrence, worsening, or becoming serious) is incomplete, an imputation algorithm will be used to classify the adverse event as pretreatment, treatment-emergent, or posttreatment. The algorithm for imputing date/time of onset will be conservative and will classify an adverse event as treatment emergent unless there is definitive information to determine it is pretreatment or posttreatment. Details on classification of adverse events with missing or partial onset dates are provided in [Section 2.5.3](#).

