Adverse event incidence tables will present by SOC, HLTG, and PT, sorted in alphabetical order, the number (n) and percentage (%) of patients experiencing an adverse event. Multiple occurrences of the same event in the same patient will be counted only once in the tables within a treatment phase. The denominator for computation of percentages is the safety population.

Analysis of all treatment-emergent adverse events

The following treatment-emergent adverse event summaries will be generated for the safety population.

- Overview of treatment-emergent adverse events, summarizing number (%) of patients with any
 - Treatment-emergent adverse event
 - Treatment-emergent AESIs
 - Serious treatment-emergent adverse event
 - Treatment-emergent adverse event leading to death
 - Treatment-emergent adverse event leading to permanent treatment discontinuation
- All treatment-emergent adverse event by primary SOC, HLTG, and PT, showing number (%) of patients with at least 1 treatment-emergent adverse event sorted by the SOC internationally agreed order. The other levels (HLTG, PT) will be presented in alphabetical order

Analysis of all treatment emergent serious adverse event(s)

- All SAEs by primary SOC, HLTG, and PT, showing number (%) of patients with at least 1 treatment-emergent adverse event sorted by the SOC internationally agreed order. The other levels (HLTG, PT) will be presented in alphabetical order

Analysis of all treatment-emergent adverse event(s) leading to treatment discontinuation

- All TEAEs leading to treatment discontinuation by primary SOC, HLTG, and PT, showing number (%) of patients with at least 1 treatment-emergent adverse event sorted by the SOC internationally agreed order. The other levels (HLTG, PT) will be presented in alphabetical order

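### The SAP drops the protocol's overview row for SAEs and fatal AEs of any timing, and does not define the counting period of the SAE/death endpoint

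*Protocol*

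**What the plan says.** Both documents carry the same secondary endpoint, in Protocol 9.2 and SAP 2.1.4: "Incidence rates for SAEs/death over the study".

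The protocol's overview (11.4.3.1.2) has two distinct SAE rows. One reads "Any SAE and AEs leading to death (regardless of treatment-emergent status"; the other reads "Any treatment-emergent SAEs".

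The overview in SAP 2.4.5.1 has "Serious treatment-emergent adverse event" and "Treatment-emergent adverse event leading to death", with no row that ignores treatment-emergent status. Further down the same section, under a heading about treatment-emergent serious events, the table by coded term is described as "All SAEs by primary SOC, HLTG, and PT, showing number (%) of patients with at least 1 treatment-emergent adverse event".

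SAP 2.4.5.1 also keeps the analysis of the secondary endpoint: "Incidence rates with corresponding 95% CI (Clopper-Pearson method) will be presented for SAEs/death over the study". SAP 2.4.5.2 keeps the protocol's count of deaths by study period, on-study deaths included.

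SAP 1.5 states that there are no modifications to the protocol's statistical section. SAP 1.6 lists only the added COVID-19 section.

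**The concern.** SAEs are a secondary endpoint of a study whose only objective is safety, and Protocol 4.2 gives late-onset events as one of its interests. The protocol planned to show every SAE and, beside it, the treatment-emergent subset, so that a reader could see what lies between the two. With the first row gone, an SAE collected outside the SAP's treatment-emergent period has no place in the overview. On the stated counting rule it has none in the coded SAE table either.

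Two further problems follow. The coded table's heading, its description and its counting rule do not agree, so two programmers could build different tables from it. And the endpoint analysis, read on its plain wording, may give an SAE percentage that differs from the one in the tables, with nothing in the SAP to explain the difference. Because SAP 1.5 declares nothing, a reader cannot tell whether the change was intended.

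**Working it through.** The plan gives no figure to reproduce: the 750 patients are a rollover expectation, and there is no assumed SAE rate. The check is therefore whether SAEs can be collected yet fall outside the treatment-emergent (TE) period.

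**Inputs**
- Collection runs from consent to the patient's end of study (Protocol 9.2, 10.4.2).
- The SAP TE period runs from first dose to last dose + 14 days for completers, or + 84 days after early discontinuation (SAP 2.3.2, 2.4.5).
- The protocol TE period runs from first dose to EOT/EOS, Visit 13 (11.3.2).
- After early discontinuation, the EOS Visit comes 12 weeks after the EOT Visit (Protocol 10.1.5).
- Dosing is every 14 ± 3 days (Protocol 8.1.3), and no drug is dispensed at Visit 13 (flow chart, note d). The last scheduled dose is therefore Week 142.

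**Window 1, consent to first dose.** Any SAE here is collected but is not treatment-emergent under either document. The flow chart puts consent and first dose at Visit 1, so this window is normally short.

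**Window 2, completers.** Gap = Visit 13 − (last dose + 14).
- On schedule: last dose 142 × 7 = day 994; TE end 994 + 14 = 1008; Visit 13 at 144 × 7 = 1008. Gap 0.
- Visit 13 seven days late (assuming the ± 7-day window given for Visits 2 to 12 also applies): 1015 − 1008 = 7 days.
- The same, with the last dose three days early: 1015 − (991 + 14) = 10 days.
- Last dose missed: 1008 − (980 + 14) = 14 days.
- Last two doses missed: 1008 − (966 + 14) = 28 days.

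**Window 3, early discontinuers.** Gap = (EOT + 84) − (last dose + 84) = EOT − last dose. An EOT Visit 14, 28 or 84 days after the last dose leaves 14, 28 or 84 days of observed follow-up outside the TE period.

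**Illustrative size (all rates, counts and mean gaps are assumptions)**
- Completers only: 60 patients × 2 weeks = 120 weeks = 2.3 patient-years; 120 patients × 6 weeks = 720 weeks = 13.8 patient-years. At 5 to 10 SAEs per 100 patient-years: 2.3 × 0.05 = 0.1 to 13.8 × 0.10 = 1.4 SAEs.
- Outer range, giving all 750 patients a mean gap of 7 to 28 days at 5 to 15 SAEs per 100 patient-years: 750 × 7/365.25 × 0.05 = 0.7 to 750 × 28/365.25 × 0.15 = 8.6 SAEs. This overstates the likely size, since a completer on schedule has no gap.
- Effect on the percentage: each added patient moves it by 1/750 = 0.13 points. If 75 of 750 had a treatment-emergent SAE, the figure is 10.0% (Clopper-Pearson 95% CI 7.95 to 12.37). One more patient gives 10.13% (8.07 to 12.52); eight more give 11.07% (8.91 to 13.53).

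**The case against.** The strongest reply is that the SAP does plan the endpoint as stated. The analysis under secondary safety endpoints carries no treatment-emergent restriction, and on-study deaths are counted separately. A reader might infer from the overview that the SAP has cut the SAE endpoint down to treatment-emergent events, or that the plan is built to make the drug look safer. The documents do not support either reading. The endpoint wording is unchanged from the protocol, and a shortened overview is no evidence of intent. This part of the reply stands. It leaves one question open: the SAP does not say what study-wide means for this endpoint, and the same section puts the primary focus of AE reporting on treatment-emergent events.

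A second reply is that the gaps hardly occur. For a completer on schedule the gap is exactly zero, and this too stands. The SAP does not define a completer, so a patient who misses final doses might be classed as an early discontinuer and get 84 days. That covers the time to Visit 13 after one missed dose (980 + 84 = 1064, beyond 1008). But if that patient then has the EOS Visit 12 weeks after an EOT Visit on day 1008, collection runs to 1008 + 84 = 1092, and 1092 − 1064 = 28 days lie outside. Reclassification moves the gap without removing it.

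A third reply is that the size rests on assumed inputs, and that a lost event changes the percentage only if the patient has no other counted SAE. Both points are right, and they limit what can be said about magnitude.

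**Conclusion.** The point holds as a mismatch between the protocol and the SAP's tables. A row that the protocol specifies is missing from the SAP overview, the coded SAE table contradicts itself, the counting period of the SAE/death endpoint is undefined, and the departure is not declared. SAEs outside the SAP's treatment-emergent period would be absent from the overview and, as worded, from the coded table. They are not expressly removed from the secondary endpoint.

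The number affected is probably small and cannot be derived from the documents. On the assumptions shown, completers contribute 0.1 to 1.4 SAEs, and 8.6 is the top of a range that gives every patient a gap. Leaving events out can only lower the SAE percentage in these tables or leave it unchanged, but nothing shows that the effect would be material. The case for the change rests on agreement between the endpoint and its tables, not on an expected shift in the result.

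**What to change.** In SAP 2.4.5.1:
- Restore the protocol's overview row for any SAE and any AE leading to death, whether or not treatment-emergent, and keep treatment-emergent SAEs as a second row.
- State that the secondary SAE/death incidence counts all SAEs and deaths in the safety population from informed consent to each patient's end of study. Starting at first dose would conflict with collection from consent and with the restored row.
- Make the coded SAE table's title and counting rule agree, preferably as one table of all SAEs and one of treatment-emergent SAEs.

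Elsewhere:
- Reconcile the treatment-emergent period in Protocol 11.3.2 with SAP 2.3.2, since that difference decides which SAEs count as treatment-emergent.
- Record any departure that is intended in SAP 1.5.

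The cost is one extra row or table and some wording. No new data are needed, because these events are already collected. The reported SAE percentage may rise slightly.

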11.4.3.1.3 Adverse events of special interest

The incidence of each AESI and the number of AESIs per 100 patient-years will be presented; AESI definitions can be found in [Section 10.4.1.3](#).

11.4.3.1.4 Death

The following summaries for deaths will be presented:

- Number (%) of patients who died by study period (TEAE, on-study) and reasons for death.
- TEAE leading to death (death as an outcome on the AE eCRF screen as reported by the Investigator) by primary SOC, HLTG, and PT showing number (%) of patients.

11.4.3.1.5 Clinical laboratory evaluations, vital signs, and physical examination findings

Clinically significant test results will be recorded as AEs; overall AE summaries will include all AEs.

11.4.4 Concomitant medications

All concomitant medications will be summarized according to the World Health Organization Drug Dictionary, by anatomic class and therapeutic category using the number (%) of patients taking the medication. Asthma controller and reliever medication use will be summarized separately, in addition to all concomitant medications used.

11.5 INTERIM ANALYSIS

Interim analyses of data may be conducted to support regulatory submissions or publication activities.

12 ETHICAL AND REGULATORY CONSIDERATIONS

12.1 ETHICAL AND REGULATORY STANDARDS

This clinical trial will be conducted by the Sponsor, the Investigator, and delegated Investigator staff and Subinvestigator, in accordance with consensus ethics principles derived from international ethics guidelines, including the Declaration of Helsinki, and the International Council for Harmonisation (ICH) guidelines for Good Clinical Practice (GCP), all applicable laws, rules and regulations.

This clinical trial will be recorded in a free, publicly accessible, internet-based registry, no later than 21 days after the first patient enrollment, in compliance with applicable regulatory requirements and with Sanofi public disclosure commitments.

12.2 INFORMED CONSENT

The Investigator (according to applicable regulatory requirements), or a person designated by the Investigator, and under the Investigator's responsibility, should fully inform the patient (and the parent[s] or guardian[s], if applicable) of all pertinent aspects of the clinical trial including the written information giving approval/favorable opinion by the ethics committee (IRB/IEC). All participants should be informed to the fullest extent possible about the study, in language and terms they are able to understand.

Prior to a patient's participation in the clinical trial, the written ICF should be signed, name filled in and personally dated by the patient, by the patient's parent(s) or by the patient's legally acceptable representative, and by the person who conducted the informed consent discussion. A copy of the signed and dated written ICF will be provided to the patient (for adult patients) or patient's parent(s) or patient's legally accepted representative for pediatric patients. Local law must be observed in deciding whether 1 or both parents/guardians consent is required. If only 1 parent or guardian signs the consent form, the Investigator must document the reason for only 1 parent or guardian's signature.

In addition, participants will assent as detailed below or will follow the ethics committee (IRB/IEC) approved standard practice for pediatric participants at each participating center (age of assent to be determined by the IRB's/IEC's or be consistent with the local requirements):

- Participants who can read the assent form will do so before writing their name and dating or signing and dating the form.
- Participants who can write but cannot read will have the assent form read to them before writing their name on the form.
- Participants who can understand but who can neither write nor read will have the assent form read to them in presence of an impartial witness, who will sign and date the assent form to confirm that assent was given.

The ICF and the assent form used by the Investigator for obtaining the Patient's Informed Consent must be reviewed and approved by the Sponsor prior to submission to the appropriate ethics committee (IRB/IEC) for approval/favorable opinion.

In relation with the population of patients exposed in the trial ie, pediatric/minor patients, the IRB/IEC should ensure proper advice from specialist with pediatrics expertise (competent in the area of clinical, ethical, and psychosocial problems in the field of pediatrics) according to national regulations. This should be documented.

12.3 HEALTH AUTHORITIES AND INSTITUTIONAL REVIEW BOARD/INDEPENDENT ETHICS COMMITTEE

As required by local regulation, the Investigator or the Sponsor must submit this clinical trial protocol to the health authorities (competent regulatory authority) and the appropriate IRB/IEC, and is required to forward to the respective other party a copy of the written and dated approval/favorable opinion signed by the chairman with IRB/IEC composition.

The clinical trial (study number, clinical trial protocol title and version number), the documents reviewed (clinical trial protocol, ICF, Investigator's curriculum vitae, etc) and the date of the review should be clearly stated on the written (IRB/IEC) approval/favorable opinion.

The IMP will not be released at the study site and the Investigator will not start the study before the written and dated approval/favorable opinion is received by the Investigator and the Sponsor.

During the clinical trial, any amendment or modification to the clinical trial protocol should be submitted to the health authorities (competent regulatory authority), as required by local regulation, in addition to the IRB/IEC before implementation, unless the change is necessary to eliminate an immediate hazard to the patients, in which case the health authorities (competent regulatory authority) and the IRB/IEC should be informed as soon as possible. They should also be informed of any event likely to affect the safety of patients or the continued conduct of the clinical trial, in particular any change in safety. All updates to the IB will be sent to the IRB/IEC and to health authorities (competent regulatory authority), as required by local regulation.

A progress report is sent to the IRB/IEC at least annually and a summary of the clinical trial's outcome at the end of the clinical trial.

13 STUDY MONITORING

13.1 RESPONSIBILITIES OF THE INVESTIGATORS

The Investigator is required to ensure compliance with all procedures required by the clinical trial protocol and with all study procedures provided by the Sponsor (including security rules). The Investigator agrees to provide reliable data and all information requested by the clinical trial protocol (with the help of the eCRF, Discrepancy Resolution Form [DRF] or other appropriate instrument) in an accurate and legible manner according to the instructions provided and to ensure direct access to source documents by Sponsor representatives.

If any circuit includes transfer of data particular attention should be paid to the confidentiality of the patient's data to be transferred.

The Investigator may appoint such other individuals as he/she may deem appropriate as Subinvestigators to assist in the conduct of the clinical trial in accordance with the clinical trial protocol. All Subinvestigators shall be appointed and listed in a timely manner. The Subinvestigators will be supervised by and work under the responsibility of the Investigator. The Investigator will provide them with a copy of the clinical trial protocol and all necessary information.

13.2 RESPONSIBILITIES OF THE SPONSOR

The Sponsor of this clinical trial is responsible to regulatory authorities for taking all reasonable steps to ensure the proper conduct of the clinical trial as regards ethics, clinical trial protocol compliance, and integrity and validity of the data recorded on the eCRFs. Thus, the main duty of the monitoring team is to help the Investigator and the Sponsor maintain a high level of ethical, scientific, technical and regulatory quality in all aspects of the clinical trial.

At regular intervals during the clinical trial, the site will be contacted, through monitoring visits, letters or telephone calls, by a representative of the monitoring team to review study progress, Investigator and patient compliance with clinical trial protocol requirements and any emergent problems. These monitoring visits will include but not be limited to review of the following aspects: patient informed consent, patient recruitment and follow-up, SAE documentation and reporting, AESI documentation and reporting, AE documentation, IMP allocation, patient compliance with the IMP regimen, IMP accountability, concomitant therapy use, and quality of data.

13.3 SOURCE DOCUMENT REQUIREMENTS

According to the ICH GCP, the monitoring team must check the eCRF entries against the source documents, except for the pre identified source data directly recorded in the eCRF. The ICF will include a statement by which the patient allows the Sponsor's duly authorized personnel, the

ethics committee (IRB/IEC), and the regulatory authorities to have direct access to original medical records which support the data on the eCRFs (eg, patient's medical file, appointment books, original laboratory records). These personnel, bound by professional secrecy, must maintain the confidentiality of all personal identity or personal medical information (according to confidentiality and personal data protection rules).

13.4 USE AND COMPLETION OF CASE REPORT FORMS AND ADDITIONAL REQUEST

It is the responsibility of the Investigator to maintain adequate and accurate eCRFs (according to the technology used) designed by the Sponsor to record (according to Sponsor instructions) all observations and other data pertinent to the clinical investigation in a timely manner. All eCRFs should be completed in their entirety in a neat, legible manner to ensure accurate interpretation of data.

Should a correction be made, the corrected information will be entered in the eCRF overwriting the initial information. An audit trail allows identifying the modification.

Data are available within the system to the Sponsor as soon as they are entered in the eCRF.

The computerized handling of the data by the Sponsor may generate additional requests (DRF) to which the Investigator is obliged to respond by confirming or modifying the data questioned. The requests with their responses will be managed through the eCRF.

